Almost half of all patients starting dialysis are now over age 65.¹ Although there is a modest survival advantage for older patients treated with dialysis, for patients with serious comorbidity, dialysis may not improve survival at all.² For example, for patients age 80-85 median survival after starting dialysis is 15.6 months, yet 20% of patients will die within three months of dialysis initiation.³ While mortality for older patients receiving dialysis is high, even patients who achieve a survival advantage will experience treatment burdens and distressing symptoms. These include time spent in dialysis; repeat hospitalizations; vascular access complications; and symptoms including pain, sleep disturbance, itching, edema, constipation, nausea and loss of appetite.⁴ For patients who forgo dialysis, there are fewer treatment-associated burdens, but symptoms are similarly formidable. Whether patients choose to initiate or forgo dialysis, older patients with life-limiting ESRD would benefit from receipt of palliative care to alleviate symptoms and clarify goals.⁵

Older adults who initiate dialysis often do so by passively accepting dialysis without making an active commitment to life-supporting treatment. Anthropologists Ann Russ and Sharon Kaufman report that this leads to confusion about treatment goals and questions such as *“Do I really need this? Can I ever get off? When will this end?”*⁶ In one Canadian study, more than 60% of older adults regretted their decision to start dialysis.⁷ Furthermore, nephrologists have financial incentives to avoid placing catheters for dialysis access, which promotes early fistula creation and generates a clinical momentum to treat kidney failure without consideration of the patient’s overall health status or goals.⁸ These systems forces likely promote use of dialysis, inhibit consideration of “no dialysis” and limit receipt of palliative care with or without dialysis.

Older patients with ESRD have an urgent need for palliative care throughout their illness trajectory, not simply at the end of life. Fewer than 6% of patients on dialysis have had the opportunity to discuss end-of-life wishes.⁹ Yet studies show most of these patients would prefer not to die in a hospital and to stop dialysis if they were to become cognitively or functionally impaired.⁹ As compared to patients with terminal cancer and heart failure, patients with ESRD are more than twice as likely to be admitted to the ICU and less than half as likely to be admitted to Hospice in the final month of life.¹⁰⁻¹² Palliative care concurrent with usual treatment has clearly-demonstrated benefits for patients throughout the course of illness by promoting advance care planning, symptom relief and less invasive treatments near death without increasing mortality.^{13,14} (Figure 1)

[figure not shown]

Figure 1: Use of palliative care over time

Current communication practices do not provide the critical information patients need to decide between dialysis and no dialysis, or recognize the value of palliative care regardless of treatment choice. Nephrologists routinely focus on electrolyte management, blood pressure medications and “treatment for when the kidneys fail,” rather than engaging patients in a discussion about overall prognosis and goals.¹⁵¹⁹ This makes it difficult for patients to associate their personal values with the likely consequences of starting dialysis. We have documented that nephrologists rarely present “supportive care” as a choice, and consideration of “no dialysis” is typically initiated by patients.^{20,21} By describing dialysis as “kidney replacement” nephrologists do not reveal how a patient might experience dialysis, or expected downstream outcomes, such as predictable changes in functional status or long-term prognosis.²² Improving conversations about dialysis may help patients to receive palliative care consultation and to support subsequent treatment decisions that align with personal goals. Although palliative care for patients with poor prognosis is supported by the American Society of Nephrologists,^{23,24} barriers to palliative care include (1) patient lack of awareness about the life-limiting nature of ESRD and (2) an illness trajectory typified by a slow overall decline with interval catastrophic events and partial recovery, not a sharp and obvious deterioration.²⁵ These barriers cannot be overcome by simply referring patients to palliative care. Uptake of palliative care is limited when patients who have frequent contact with clinicians are unable to comprehend the value of an additional clinical visit. Patients who are more informed about the experience of dialysis and their overall health trajectory might take advantage of palliative care earlier in their course of illness.

Older adults need information to make decisions about life-sustaining treatments (dialysis) contextualized into their personal story. Using a strategy called scenario planning and Elwyn’s conceptual model for shared decision making,^{26,27} we have developed the Best Case/Worst Case communication tool. It is designed specifically for face-to-face clinical interactions to promote dialogue and to generate goal-concordant treatment decisions in the context of life-limiting illness. This tool is distinct from other decision aids that educate and activate patients for decision making before meeting with a clinician.^{28,29} The Best Case/Worst Case communication tool uses *scenario planning* to facilitate decision making in the setting of uncertainty. Scenario planning was originally developed in the 1950s by the Department of Defense and the RAND Corporation for military planning. It was then popularized for broader use by Pierre Wack^{30,31} an economist at Shell Oil, to translate vast probabilistic information into narrative description to facilitate strategic decisions. Rather than emphasizing precise isolated risks, this technique generates multiple plausible futures, prompting decision makers to visualize what might happen under different sets of assumptions. Scenario planning is distinct from standard-practice risk prediction and prognostication. By highlighting the interaction between forces that drive change and providing an organized way to consider alternative futures, it promotes insight.³² Although it has been successfully applied to a wide range of decisions in business and government, scenario planning is not widely used in the clinical setting.

We have adapted the practice of scenario planning for healthcare decision making in the Best Case/Worst Case communication tool.³³ We posit that well-constructed scenarios (personalized stories about possible futures) will appeal to the deeply held concerns of patients, encourage them to comprehend a new,

previously unimaginable reality and prepare for major shifts in a way that simple prognostication (forecasting) cannot.

How the Best Case/Worst Case tool works: The clinician verbally describes the “best case,” “worst case,” and “most likely” stories about the experience of each treatment option—incorporating rich narrative from clinical experience and patient-specific relevant outcomes—while drawing a graphic aid of those options (Figure 2). Vertical bars represent treatment options; their length shows the range of outcomes and the magnitude of the difference between the “best case” (star), the “worst case” (box) and a “most likely case” (oval). The clinician also writes short notes about each option on the diagram, which helps the patient recall details of the conversation later. The narrative

description and graphic aid help the patient formulate and express preferences. From this exchange, the clinician can then provide a treatment recommendation that is grounded in the relevant clinical context and reflects the patient’s values. A copy of the graphic aid is stored in the patient’s chart. Patients also retain the graphic aid to discuss options with family and to support future conversations with their nephrologist and other clinicians. This approach—using a personalized information and a graphic aid—are best practices to improve understanding of complex health information, especially for persons with low health literacy.^{34,35}

We expect that use of the Best Case/Worst Case communication tool will help nephrologists and patients identify the need for palliative care whether or not patients choose to initiate dialysis. Nephrologists can use this tool to illustrate treatment options, acknowledge uncertainty, and convey a clear message about prognosis. By using scenario planning to translate evidence about the patient’s overall health—including symptoms, events like hospital admissions and prognosis—within narratives about different possible futures, nephrologists can elicit patient preferences about specific health states and recommend goal-concordant treatment. Moreover, scenario planning allows patients to anticipate unwanted events, thus enabling nephrologists to facilitate a palliative care consultation to alleviate symptoms and clarify care goals regardless of the patient’s dialysis decision.

[figure not shown]

Figure 2: Example graphic aid for “Best Case/Worst Case”

Teaching nephrologists to use the Best Case/Worst Case communication tool has potential to increase receipt of palliative care and reduce intensive treatments at the end of life via multiple pathways. (Figure 3): first, via direct

provision of information about prognosis and health trajectory, second, through improving the quality of communication about options and outcomes, and third, via improving decision making about dialysis

initiation. Our primary outcome is receipt of palliative care and intensity of treatment at the end of life. We will assess whether patients' palliative care needs were met by measuring the patient's change in health-related quality of life over time. We will measure the impact of upstream outcomes and events that may mediate receipt of palliative care including patient and caregiver-reported assessment of quality of communication and the patient's decision to initiate or forgo dialysis.

[figure not shown]

Figure 3: Theoretical framework behind the Best Case/Worst Case intervention and this proposal

Specific aims

- Aim 1: To test the effect of the Best Case/Worst Case intervention on (1) receipt of palliative care and (2) intensity of treatment at the end of life for older patients with ESRD. We will compare (1) receipt of palliative care within 12 months of enrollment and (2) intensive care unit admissions, hospitalizations and emergency department visits in the last 30 days of life. Receipt of palliative care is the primary outcome for this study.
- Aim 2: To test the effect of the Best Case/Worst Case intervention on quality of life of older patients with ESRD. We will use the Functional Assessment of Chronic Illness Therapy – Palliative Care scale to measure quality of life at baseline, and every three months for up to two years after study enrollment.
- Aim 3: To test the effect of the Best Case/Worst Case intervention on the quality of communication between nephrologists and patients. We will use the Quality of Communication scale, which includes measurement of end-of-life communication. We will also use this patient and caregiver-reported measure to explore the mediating effect of provider communication on downstream health outcomes.

Study design

This is a multi-site, cluster-randomized clinical trial supported by the infrastructure of the Palliative Care Research Cooperative Group (PCRC). It is a parallel randomization trial with a wait-list control, randomizing nephrologists within each site to receive the intervention at study initiation or after study completion. We will enroll a total of 320 pre-dialysis patients with an estimated glomerular filtration rate (eGFR) of less than 20mL/min/1.73M² who are age 60 and older and have an estimated survival of 18 months or less.³⁶ We expect eight sites are required to ensure complete enrollment (one enrollment plan for example, 8 sites x 4 nephrologists per site with 10 patients per nephrologist = 320). (Note: two sites were added in 2022, for a total of ten sites.) We will follow patients for up to two years after study enrollment. At the start of the study, within each site, nephrologists are randomized to the control or intervention group in a ratio of 1:1. A block randomization scheme will be utilized with blinded block size. Nephrologists assigned to the intervention group will receive training on how to use the Best Case/Worst Case communication tool. Patients in the control group will receive usual care; patients in the intervention group will receive care from their nephrologist trained to use the Best Case/Worst Case communication tool. Palliative care will be available to all patients.

Table: Outcomes Measures for Each Aim				
Construct	Specific Measure	Type; range	Source	Timing
Aim 1: receipt of palliative care and intensity of treatments received at the end of life				
Receipt of palliative care	Any palliative care consult within 12 months of enrollment	Binary; 0/1	Chart review	T0 to 12 mo
Intensity of treatment	ICU admission within 30 days of death	Binary; 0/1	Chart review	T3 minus 30d.
Aim 2: Health-related Quality of Life				
Health related quality of life	Functional Assessment of Chronic Illness Therapy-Palliative Care Version 4 (FACIT-Pal)	Continuous; 0-184	Patient	T2a.... T2h
Aim 3: Quality of Communication				
Quality of Communication	Quality of Communication Questionnaire (QOC)	Continuous; 0-10	Patient	T1
Secondary Outcomes and Follow-up Measures				
Receipt of palliative care	Receipt of any palliative care during study period Hospice enrollment New documentation of advance care planning	Binary; 0/1 Binary; 0/1 Binary; 0/1	Chart review Chart review Chart review	T0 to 2 yr. T0 to 2 yr. T0 to 2 yr.
Intensity of treatment	ER visit, ICU or hospitalization within 30 days of death Surgical procedures within 30 days of death	Binary composite; 0/1 Count	Chart review Chart review	T3 minus 30d. T3 minus 30d.
Dialysis	Initiation of dialysis, Withdrawal of dialysis	Binary; 0/1	Chart review	T0 to 2 yr.
Death	Patient death	Time to event	Chart review and family report	T3
Bereavement	Quality of Dying and Death (QODD) survey	Continuous; 0-100	Caregiver	T4
Health related quality of life	Cambridge Palliative Audit Schedule (CAMPAS-R) (Caregiver QOL)	Continuous; 0-100	Caregiver	T2a.... T2h
Quality of Communication	Quality of Communication Questionnaire (QOC) (Family member version)	Continuous; 0-10	Caregiver	T1
Practitioner Opinion Survey	Nephrologist perceptions of the communication tool	Continuous; 0 - 15	Nephrologist	Study Completion

mo. = months, yr. = year, d. = day, T0 = enrollment, T1 = 48 hours after enrollment, T2 is every 3 months for up to 2 years, 2_a-2_h = repeated measures every 3 months, T3 = patient death, T4 = 3 months after patient death.

Blinding

Patients and caregivers will be blinded to the objectives of this study. They will be told that the study goal is to evaluate doctor-patient communication. Nephrologists will not be blinded to study group. We will inform all participating nephrologists about the goals of this study. Specifically, this is a study testing an intervention to improve communication about dialysis initiation and to support patient access to palliative care. We will make every effort to blind study staff, yet it is impossible to ensure that study staff will be completely blinded to intervention group. To reduce the possibility of study staff exposure to the nephrologist's randomization assignment we will coordinate the intervention allocation centrally through UW and provide regular reminders to nephrologists that they should avoid revelation of their training to study staff. To decrease ascertainment bias, study staff will adhere to a strict study script during interactions with nephrologists and during survey administration with patients and caregivers. To standardize chart abstraction, we will create a detailed abstraction protocol with data dictionary, and the UW team will train study staff to use the REDCap electronic database. We will ensure data quality by

independent abstraction and double data entry of 10% by the site PI or a suitable designee. We will compare the two abstractions and correct and retrain as needed.

Data and Safety Monitoring Plan

No formal interim analyses are planned during this study, and all study outcomes will be assessed at the completion of study follow-up.

Meetings of the DSMB will be held at least two times a year at the call of the Chairperson. DSMB interim report templates will be prepared by a study statistician with assistance from the PCRC and the Data, Informatics and Statistics Core (DISC), to be reviewed by the DSMB members at the first meeting.

Analysis of Primary Outcome

The sample size estimate, 320 patients (160/group), is based on the primary hypothesis that patients in the intervention arm will be more likely to receive palliative care and will have fewer intensive treatments at the end of life. We aim to recruit 32 nephrologists, each treating on average 10 study patients. We estimate a 10% attrition rate for study participation and that 80% of patients will die during the 2-year study period. This study is powered to detect a 10-15% absolute difference in the care patients receive, consistent with other interventions designed to effectively increase access to palliative care.³⁷⁻⁴⁰

Smaller differences are unlikely to be considered meaningful to clinicians, patients or researchers.⁴¹ We desire a two-sided type I error rate of 0.05 and estimate that the between-physician variance is around 10%. We plan to use fixed effects to account for clustering by site because it is faithful to our study design and controls for confounding related to imperfect randomization due to site imbalances better than a random effects model. Assuming the baseline rate of palliative care is 10%,^{42,43} we will have a power of 90% to detect a 14.7% increase and a power of 80% to detect a 12.9% increase in the rate of palliative care received.

General Analysis Plan

Primary Outcome

1. For receipt of **palliative care consult within 12 months of study enrollment**, for each treatment arm, we will report the sample counts and percentages. The denominator for each proportion will include all randomized subjects to the respective treatment arm. The treatment effect will be assessed using a Likelihood Ratio Test (LRT) of the fixed effect from the proportional odds cumulative incidence model, incorporating the competing risk of death.⁴⁴ The model will include a random-intercept for physician, and will include fixed effects for: site, comorbidity, and baseline functional status.

Null Hypothesis: After accounting for baseline differences, there is no difference in the receipt of palliative care consult within 12 months of study enrollment between control patients and Best Case/Worst Case intervention patients.

Alternative Hypothesis: After accounting for baseline differences, there is a difference in the receipt of palliative care consult within 12 months of study enrollment between control patients and Best Case/Worst Case intervention patients.

Secondary outcomes:

1. For **receipt of palliative care during 2-year follow up**, for each treatment arm, we will report the sample counts and percentages (this outcome is in addition to the primary outcome). The denominator for each proportion will include all subjects randomized to their respective treatment arm. The treatment effect will be assessed using a LRT of the fixed effect from the proportional odds cumulative incidence model, incorporating the competing risk of death. The model will include a random-intercept for physician, and will include fixed effects for: site, comorbidity, and baseline functional status.

Null Hypothesis: After accounting for baseline differences, there is no difference in the proportion of receipt of palliative care between control patients and Best Case/Worst Case intervention patients.

Alternative Hypothesis: After accounting for baseline differences, there is a difference in the proportion of receipt of palliative care between control patients and Best Case/Worst Case intervention patients.

2. For proportion of **ICU admissions within 30 days of death**, for each treatment arm, we will report the sample counts and percentages. The denominator for each proportion will include subjects randomized to their respective treatment arm that died within the study period. The treatment effect will be assessed using a LRT of the fixed effect from the logistic mixed-effects model. The logistic mixed-effects model will include a random-intercept for physician, and will include fixed effects for: site, comorbidity, and baseline functional status.

Null Hypothesis: After accounting for baseline differences, there is no difference in the proportion of patients with an ICU admissions within 30 days of death between control patients and Best Case/Worst Case intervention patients.

Alternative Hypothesis: After accounting for baseline differences, there is a difference in the proportion of patients with an ICU admissions within 30 days of death between control patients and Best Case/Worst Case intervention patients.

3. For the **FACIT-Pal total score patient reported health related quality of life** (score range 0-184, 46 items, survey questions 1-46), for each treatment arm, we will report the mean and standard deviation of the **FACIT-Pal total score at last follow-up** (either 2 years of follow-up or last administered survey prior to death, whichever occurs first). The treatment effect will be assessed using a LRT of the fixed effect from the linear mixed-effects model. The linear mixed-effects model will include a random-intercept for physician, and will include fixed effects for: baseline FACIT-Pal total score, site, comorbidity, and baseline functional status.

Null Hypothesis: After accounting for baseline differences, there is no difference in the average FACIT-Pal total score at last follow-up between control patients and Best Case/Worst Case intervention patients.

Alternative Hypothesis: After accounting for baseline differences, there is a difference in the average FACIT-Pal total score at last follow-up between control patients and Best Case/Worst Case intervention patients.

4. For the **FACIT-Pal total score patient reported healthy quality of life** (score range 0-184, 46 items, survey questions 1-46), for each treatment arm, we will report the mean and standard deviation of the **score slopes** (difference in baseline and either 2 years of follow-up or last administered survey prior to death, whichever occurs first, divided by the length of follow-up). The treatment effect will be assessed using a LRT of the fixed effects from the linear mixed-effects model. The linear mixed-effects model will include a random-intercept for physician, and will include fixed effects for: site, comorbidity, and baseline functional status.

Null Hypothesis: After adjusting for baseline differences, there is no difference in the slope of the FACIT-Pal total score between control patients and Best Case/Worst Case intervention patients.

Alternative Hypothesis: After adjusting for baseline differences, there is a difference in the slope of the FACIT-Pal total score between control patients and Best Case/Worst Case intervention patients.

5. For the **FACT-G total score patient reported health related quality of life** (score range 0-108, 27 items, survey questions 1-27), for each treatment arm, we will report the mean and standard deviation of the **FACT-G total score** at last follow-up (either 2 years of follow-up or last administered survey prior to death, whichever occurs first). The treatment effect will be assessed using a LRT of the fixed effect from the linear mixed-effects model. The linear mixed-effects model will include a random-intercept for physician, and will include fixed effects for: baseline FACT-G score, site, comorbidity, and baseline functional status.

Null Hypothesis: After accounting for baseline differences, there is no difference in the average FACT-G score at last follow-up between control patients and Best Case/Worst Case intervention patients.

Alternative Hypothesis: After accounting for baseline differences, there is a difference in the average FACT-G score at last follow-up between control patients and Best Case/Worst Case intervention patients.

6. For the **FACIT-Pal palliative care subscale (PalS) patient reported health related quality of life** (score range 0-76, 19 items, survey questions 28-46) for each treatment arm, we will report the mean and standard deviation of the subscale composite scores for **PalS** at last follow-up (either 2 years of follow-up or last administered survey prior to death, whichever occurs first). The treatment effect will be assessed using a LRT of the fixed effect from the linear mixed-effects model. The linear mixed-effects model will include a random-intercept for physician, and will include fixed effects for: baseline Pal score, site, comorbidity, and baseline functional status.

Null Hypothesis: After accounting for baseline differences, there is no difference in the average PalS score at last follow-up between control patients and Best Case/Worst Case intervention patients.

Alternative Hypothesis: After accounting for baseline differences, there is a difference in the average PalS score at last follow-up between control patients and Best Case/Worst Case intervention patients.

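### The SAP claims power for a 10-15 point difference, but its own figures reach 80% power only at 12.9 points and imply about 61-64% at 10 points

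*SAP*

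**What the plan says.** In Analysis of Primary Outcome the SAP plans 320 patients (160 per group) under 32 nephrologists with about 10 patients each, and a two-sided type I error of 0.05. It says "This study is powered to detect a 10-15% absolute difference in the care patients receive", with no power level attached, and continues: "Smaller differences are unlikely to be considered meaningful to clinicians, patients or researchers".

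Later in that section, from an assumed 10% control rate, it says "we will have a power of 90% to detect a 14.7% increase and a power of 80% to detect a 12.9% increase"; the outcome there is receipt of palliative care. Two inputs to that calculation are loosely stated:

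- **Clustering.** The authors "estimate that the between-physician variance is around 10" per cent, with no scale given.
- **Attrition.** "We estimate a 10% attrition rate for study participation". The outcome comes from chart review, and under General Analysis Plan, Primary Outcome, "The denominator for each proportion will include all randomized subjects to the respective treatment arm".

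On outcome status, the paragraph before Specific aims says "Our primary outcome is receipt of palliative care and intensity of treatment at the end of life". The primary hypothesis behind the sample size is that intervention patients "will be more likely to receive palliative care and will have fewer intensive treatments at the end of life". Aim 1 and the Primary Outcome list name receipt of palliative care alone. ICU admission within 30 days of death is item 2 under Secondary outcomes, and the composite of emergency visit, ICU stay or hospitalization is item 12.

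**The concern.** The range and the calculated figures do not agree. The sentence after the range makes its lower end the smallest difference of interest, so a reader will take 10 points as an effect the trial is sized to find. By the SAP's own figures it is not, at either power level the SAP uses. If the true gain were 10 points, a non-significant result would be quite likely, and the range sentence would invite the reading that such a gain had been ruled out.

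The outcome wording is a smaller matter. Two sentences present treatment intensity as part of the primary outcome or hypothesis, although the power figures cover palliative care only and the formal lists make intensity secondary.

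**Working it through.** **Inputs (Analysis of Primary Outcome).** Control rate p1 = 0.10; two-sided alpha 0.05 (z = 1.960); 160 per arm; 16 nephrologists per arm with 10 patients each; 80% power at +12.9 points (p2 = 0.229) and 90% at +14.7 points (p2 = 0.247). The increases are read as absolute percentage points, as the range sentence says.

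**1. Reproducing the stated pair.** Assume the 10% variance is a random-intercept variance of 0.1 on the logit scale.

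- *Log-odds Wald test, 160 per arm, 10 per nephrologist.* Variance per cluster = 0.1 + 1/(m·p·(1-p)), and SE = √[(sum over the two arms)/16]. At 12.9 points the log odds ratio is 0.983 and the SE 0.343, giving 81.9% power. At 14.7 points power is 89.0%.
- *Design effect 1 + (m-1)·ICC, 144 per arm after 10% attrition, m = 9.* Logit variance 0.1 converts to an ICC of 0.009 at 10% and 0.017 at 22.9%. Unpooled power is 81.0% at 12.9 points and 88.7% at 14.7.

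Both are within 2 points of the stated 80% and 90%, so the pair is approximately reproducible on this reading.

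**2. Power at 10 points, from the stated pair alone.** No assumption about variance or attrition is needed. Effective n per arm (unpooled) = (z_alpha + z_power)² · [p1(1-p1) + p2(1-p2)] / (p2-p1)².

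- From 80% at 12.9: 7.849 × (0.0900 + 0.1766) / 0.129² = 125.7.
- From 90% at 14.7: 10.507 × (0.0900 + 0.1860) / 0.147² = 134.2.

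Power at 10% v 20% = Φ(0.10 / √(0.25/n) - 1.960).

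- n = 125.7: Φ(2.242 - 1.960) = 0.611.
- n = 134.2: Φ(2.317 - 1.960) = 0.639.

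Pooled-variance and arcsine versions give effective n of 125-137 and agree closely:

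| True difference | Power implied by the stated pair |
|---|---|
| 10 points | 61-64% |
| 11 points | 68-71% |
| 12 points | 75-78% |
| 12.9 points | 80-83% |
| 14.7 points | 88-90% |

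The two models in step 1 give 64.5% (log-odds) and 62.4-63.2% (design effect; unpooled, pooled and arcsine) at 10 points.

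**3. Ceiling.** With 160 per arm, no clustering and no loss: Φ(0.10/√(0.25/160) - 1.960) = Φ(0.570) = 71.6% (70.9% pooled, 71.8% arcsine). Reaching 80% at 10 points would need 7.849 × 0.25 / 0.01 = 196 per arm (195-199 across formulas), still with no clustering or loss.

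**4. If an ICC of 0.10 was meant.** Effective n per arm is 160/(1 + 9 × 0.10) = 84.2, or 144/(1 + 8 × 0.10) = 80.0 with attrition.

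| | 80% power | 90% power |
|---|---|---|
| 160 per arm | 16.2-16.6 points | 19.3-19.7 points |
| 144 per arm | 16.7-17.1 points | 19.8-20.3 points |

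This reading does not reproduce 12.9 and 14.7. Power at 10 points would be 42-45%.

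**5. Outcome labels side by side.**

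- Intensity worded as primary: the paragraph before Specific aims, and the primary hypothesis in Analysis of Primary Outcome.
- Palliative care alone as primary: Aim 1 and the Primary Outcome list. ICU admission and the intensity composite stand under Secondary outcomes.
- Exploratory analyses, item 3 (mediation), names its two outcomes clearly but labels both primary.
- Exploratory analyses, items 1 and 2, refer to primary outcomes for Aims 1 to 3. The outcomes table narrows these to FACIT-Pal and QOC for Aims 2 and 3. It does not choose between the FACIT-Pal analyses (Secondary outcomes items 3 and 4) or the QOC scores (items 7, 8 and 9).

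**The case against.** The strongest reply is that nothing has been miscalculated. The range sentence carries no power level, both exact figures lie inside 10-15, and they appear in the same section, so the range may be only a rounded bracket. That the calculated pair is sound on the logit-scale reading stands. The bracket reading would be acceptable if the next sentence did not treat anything smaller as unimportant. As written, the bottom of the range becomes the threshold of interest, and the trial is not sized for it.

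A second reply is that 61-64% is an unadjusted approximation, whereas the planned test is a likelihood ratio test from a covariate-adjusted competing-risks model. The two stated pairs also back-solve to slightly different effective sizes. Both facts are true, and the exact figure should come from the trial statistician. Across the logit-variance models, without or with attrition, power at 10 points runs from 60% to 67%, so the conclusion does not turn on the formula.

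Third, what a null result excludes depends on its confidence interval, not on this sentence. That is correct, and it limits the harm to misreading. Finally, Aim 1 and the outcome lists already settle which outcome is primary, and the ICC of 0.10 is a reading that the SAP's own figures argue against. Both points hold, and both matters are treated here as lesser ones.

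**Conclusion.** The concern holds. The SAP's figures support 80% power from 12.9 points upward, not from 10. The unsupported part is 2.9 of the 5 points in the range, and power at its lower end is about 61-64%. This rests on the SAP's 10% control rate, its two stated power figures and a two-proportion approximation to the planned test. It does not depend on how the between-physician variance or the attrition is read, because even the unadjusted no-clustering, no-loss ceiling is about 72%.

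The stated 12.9 and 14.7 are not shown to be wrong; they would be only if an ICC of 0.10 was intended. The wording that makes treatment intensity primary is inconsistent with the single primary outcome, but this is a labelling matter. The unstated variance scale, the attrition handling and the choice of FACIT-Pal and QOC analyses are missing detail, and the conclusion does not rest on them.

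**What to change.** In Analysis of Primary Outcome, replace the range sentence with a statement such as: *the study has 80% power for a 12.9-point and 90% power for a 14.7-point absolute increase in receipt of palliative care; power for a 10-point increase is about 60-65%*. The trial statistician should confirm the last figure with the method behind the other two.

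Remove treatment intensity from the primary hypothesis in that section and from the primary-outcome sentence before Specific aims. If the assumption that 80% of patients will die is kept, tie it to the secondary outcomes whose denominator is deaths.

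While editing, it would also help to:

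- state the scale of the between-physician variance and whether the 10% attrition is in the calculation; if an ICC of 0.10 was meant, recalculate the detectable differences (about 16-17 points for 80% and 19-20 for 90%);
- in the mediation analysis, name the 12-month palliative care consult and ICU admission within 30 days of death instead of calling both primary;
- in the per-protocol and heterogeneity analyses, say which FACIT-Pal analysis (item 3 or 4) and which QOC score (item 7, 8 or 9) is meant.

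The cost is SAP wording and a less favourable power statement. No extra patients are needed, and the analysis of the primary outcome is unchanged.
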